1.0 Background & Rationale

Alcohol use disorder (AUD; formerly termed alcohol dependence or addiction), is a chronic disorder that includes 1) compulsivity in and lack of control over alcohol seeking and consumption, 2) the development of tolerance, and eventually 3) the emergence of withdrawal (including physical and affective symptoms when alcohol is restricted). It is among the most common and costly mental health problems¹⁻⁴. FDA-approved medications for alcohol dependence have had only modest efficacy and have been minimally used^{5,6}. AUD is theorized to progress through three overlapping stages: binge-intoxication, preoccupation-anticipation, and withdrawal-negative affect⁷. Binge-intoxication is thought to consist of frequent ingestion of alcohol to achieve a pleasurable, inebriated state. Because of chemical adaptations in the brain with repeated alcohol exposure (neuroadaptations), achieving intoxication requires ingestion of steadily increasing amounts of alcohol, a process referred to as tolerance formation. While associated changes in activity of some brain neurotransmitter systems have been found, the precise mechanisms of alcohol tolerance formation remain poorly understood^{8,9}. During the **preoccupation-anticipation** stage, drinking is increasingly driven by compulsion rather than pleasure. Sustained, heavy drinking leads to increasing tolerance, and eventually physiologic alcohol dependence. At this stage, cessation of drinking produces unpleasant, potentially fatal, withdrawal symptoms because the neurochemical balance in the alcohol-adapted brain is abruptly disrupted. In the withdrawal**negative affect** stage, avoiding the discomfort of withdrawal, rather than seeking pleasurable inebriation, may become the primary motivation to continue heavy drinking^{10,11}.

Oxytocin (OT) is a small protein that is both a neurotransmitter in the brain and a hormone released into the blood from the pituitary gland. Because numerous studies in animals and, more recently, in humans have found a wide variety of prosocial effects of OT that are exerted in the brain, it has become known in the popular culture as the "love" hormone¹²⁻¹⁴. In humans, nasal OT administration has been shown in some studies to increase interpersonal trust and cooperation as well as accurate interpretation of social cues such as facial expressions¹⁵⁻¹⁷.

However, animal research has also suggested some potentially clinically useful effects of OT on alcohol use and abuse. Numerous preclinical studies have shown that OT treatment: 1) prevents tolerance formation to repeated doses of alcohol non-dependent animals; 2) blocks withdrawal seizures in alcohol-dependent animals, and 3) in a recent study, results in decreased motivation for alcohol in alcohol-dependent animals¹⁸⁻²⁴. For example, when non-dependent mice are given an impairing dose of alcohol on successive days, they adapt and steadily improve on daily tests of balance and coordination conducted after each alcohol dose. However, when OT is given before each alcohol dose, the development of tolerance is inhibited and balance and coordination improves more slowly on daily tests¹⁸. Treatment with the GABA-antagonist picrotoxin triggers withdrawal seizures in alcohol-dependent mice, an effect reduced by OT administration²³. More recently, OT administration reduced motivation for alcohol and alcohol self-administration in alcohol dependent rats but not non-dependent animals²⁴.

In alcohol-dependent, heavy drinking individuals, studied on a research unit, [name] and colleagues recently discovered that twice-daily OT treatment (given in a nasal spray that results in significant brain delivery) potently and rapidly blocked alcohol withdrawal as judged by a decreased need for lorazepam intervention²⁵. This, to the knowledge of the investigators, is the only journal publication on OT treatment of human AUD. [name] and colleagues have also recently completed a National Institute of Alcohol Abuse and Alcoholism (NIAAA) funded, randomized, placebo-controlled clinical trial; preliminary analysis found that 12 weeks of twice-daily intranasal administration of OT significantly decreased heavy-drinking days (5 standard drinks/day for men and 4 for womer; a standard drink contains the same amount of alcohol as a 12 oz. beer) in heavy-drinking individuals. Other non-treatment examinations of the human response to OT in the context of an alcohol exposure or an AUD is limited, yet informative. While no effect of OT on the subjective response to alcohol was identified in light or social drinkers^{26, 27}, OT was reported to benefit baseline interoceptive accuracy

in heavy drinkers²⁷. In contrast, when examined in veterans with comorbid post-traumatic stress disorder and AUD, OT was found to only marginally reduce stress reactivity (a core non-tolerance feature of the later stage of withdrawal-negative affect), and did not reduce self-reported craving²⁸. Similarly, OT was not found to reduce emotional reactivity during a conflict task in couples with substance misuse²⁹. These human studies, in conjunction with our own, suggest that: OT acts upon chronic tolerance, would be most effective in heavy drinkers, and its assessment should include subjective response to alcohol and craving, as well as objective measures of cognition and behavior.

Based on OT effects in rodents, and the available human literature, we hypothesize that OT may exert therapeutic effects by rapidly reversing alcohol-induced neuroadaptations in the brain. This putative reduction of tolerance would represent a unique approach to treatment that could revolutionize clinical AUD care. If clinicians could reduce or eliminate tolerance, it would mitigate one of the key drivers of relapse. Furthermore, the availability of a treatment that reduces acute withdrawal and risk of relapse would provide a continuum of medical care that is now lacking. The proposed project will directly test whether OT reverses tolerance and associated alcohol seeking in humans by employing state-of-the-art computer-assisted intravenous alcohol administration. Two separate experiments will be run, one of which combines a standardized breath and therefore brain alcohol exposure with sensitive tests of subjective response and cognitive function. The second is an alcohol self-administration paradigm, assessing objective change in motivation for alcohol. Demonstrating that OT (compared to placebo, PL) worsens test performances in alcohol-dependent individuals and/or reduces the compulsive drive to self-administer alcohol would be strong evidence for its potential AUD treatment utility.

2.0 Objective(s)

The goal of this project is to provide evidence supporting the hypothesis that intranasal OT treatment blocks or reduces tolerance to alcohol and motivation for alcohol in heavy drinking individuals. Evidence supporting either outcome would indicate that OT has a potentially novel therapeutic effect and would then be used in a subsequent, larger study of the effect. Such an outcome would open new fields of investigation into a potential role for OT in AUD treatment, notably the prevention of relapse and support of abstinence. This could have profound effect on treatment approaches for AUDs. The project will examine whether OT reverses tolerance and associated alcohol seeking in humans. Tolerance to and motivation for alcohol will be assessed with sensitive tests of subjective response and cognitive function tested prior to, at the beginning, and at the end of an intravenous alcohol BrAC clamp (a standardized brain alcohol exposure). Alcohol seeking will be tested using a progressive ratio alcohol self-administration paradigm, assessing objective change in motivation for alcohol.

2.1 Primary Objective:

Aim 1: Demonstrate that OT alters alcohol tolerance. This will be assessed using a within-subjects design comparing OT and PL infusion sessions. Cognitive, motor and subjective responses will be tested prior to, at the beginning, and at the end of a steady-state alcohol clamp.

2.2 Secondary Objective:

Aim 2: Demonstrate that OT decreases motivation for alcohol. Motivation for alcohol will be measured directly when participants will be able to earn standardized alcohol exposures by performing a button pressing task on a progressive ratio scale in the active versus control condition. Motivation will also be assessed by measures given during the clamp (and its respective baseline and control assessments) including an alcohol purchase task (APT) that assesses the value of alcohol from a behavioral economics perspective and measures of subjective perception and craving for alcohol.

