3.0 Outcome Measures/Endpoints

3.1 Primary Outcome Measures:

Aim 1: OT will alter alcohol tolerance. Compared to their performance under PL and respective baseline assessment, participants given intranasal OT will show, in one or more of the following, greater alcohol-related perturbation of the subjective response to alcohol, the Stroop test, and Stop Signal task performance.

3.2 Primary Outcome Measures:

Aim 2: OT will reduce motivation for alcohol. Participants will display lower motivation for alcohol under OT compared to PL, reflected by one of more of the following: During alcohol self-administration, less cumulative work for alcohol on the progressive ratio task, and reduced overall alcohol exposure as reflected by the breath alcohol concentration (BrAC) curve during alcohol self-administration; During the BrAC clamp, altered APT derived behavioral economic indices and/or reduced subjective craving for alcohol.

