Session procedures: Self-administration (Figure 4). During the 150 min alcohol self-administration session, the participant initiates each work-set by choosing between 1 of 2 rewards, either alcohol or water. Work-sets consist of trials of the Constant Attention Task, or CAT (Figure 5), developed by our laboratory and with demonstrated sensitivity to pharmacogenomics and sex effects^{38, 39}. Successive rewards require an increasing number of successful CAT trials. The work schedules required to obtain water or alcohol are identical, but progress is tracked separately and not communicated to the participants. Throughout any workset, participants are free to wait, work ad-lib, pause, or cease working. The available rewards are a standardized increment in BrAC (alcohol, labeled "A") or an infusion of saline (water, labeled "W"), each delivered over 2.5 min. Reward delivery begins immediately after the last correct CAT trial required for the work-set is performed. Alcohol reward increments raise the participant's BrAC by 10.0 mg/dL in 2.5 min before declining at a steady rate of -0.8 mg/dl/min, until the next alcohol reward is delivered or as long as pharmacokinetically possible. CAIS continuously estimates the future time course of BrAC and prohibits infusion that would vield a BrAC exceeding the predetermined, ecologically valid safety limit (180 mg/dL in this heavy alcohol drinking sample). The first dose of OT or PL will be administered 30 min before the start of the self-administration phase, and consist of 10 intranasal puffs [insufflations] alternating every 30 seconds between nostrils, delivering in total 40 IU of OT in 1 ml of solution or 1 ml of PL solution. Booster doses of 24 IU of OT will be given approximately hourly after the initial dose. Participants will complete the subjective perceptions assessment and side effects questionnaire prior to the first OT/PL administration, immediately before the start of alcohol self-administration, and at 20 min intervals throughout the session, timed with alcohol reward increments when possible. Except for ad-libitum bathroom breaks, participants remain in the chamber or room for the duration of the experiment; technician interaction is limited to occasional BrAC samples, data collection, and verbal checks to assure subject comfort at the beginning/end of each intervention.

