12.0 Statistical Considerations

The primary goal of the study is to generate data that would be supportive of a large, properly powered study of the effects of OT on tolerance and/or motivation for alcohol. For this exploratory study, we anticipate examining within-subject effects of OT compared to PL using paired t-tests, accommodating baseline assessments as appropriate for the specific measures.

Aim 1 Hypothesis Testing Plan

Hypothesis 1: Tolerance to alcohol will be altered by OT, such that participants exhibit greater effects of alcohol when tested with OT compared to PL and each with respect to its own baseline assessment. Specifically, we predict the following differences in one or more of the following measures:

Stop Signal Response Task: Participants will have more rapid reaction times under PL compared to OT. Subjective Perceptions of Alcohol and Craving Participants will report weaker subjective effects of alcohol and higher craving under PL compared to OT. Stroop Test Participants will have shorter response times and fewer errors under PL compared to OT.

Aim 2 Hypothesis Testing Plan

Hypothesis 2: OT will reduce motivation for alcohol as demonstrated by changes in one or more of the following measures:

Alcohol Purchase Task

Participants will display alteration in behavioral economic indices derived from the Alcohol Purchase task under OT compared to PL (for example, a reduction in intensity, greater elasticity, lower breakpoint, lower total outcome, etc.).

Subjective Perceptions of Alcohol and Craving

Participants will report weaker subjective effects of alcohol and higher craving under PL compared to OT. Alcohol Self-Administration

Participants will demonstrate reduced cumulative work for alcohol rewards and less overall alcohol exposure under OT compared to PL.

Missing Data

Missing data may occur intermittently or due to attrition. Due to the within-subjects design, participants completing only one of two experimental sessions will be excluded from final analyses.

Power Analyses

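### Less work or lower BrAC under OT is read as lower motivation, but the reduced tolerance predicted by Aim 1 could produce the same pattern, and no analysis is planned to set the two apart

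*Combined protocol and SAP*

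**What the plan says.** Section 2.2 presents progressive-ratio work as a direct reading of motivation: "Motivation for alcohol will be measured directly when participants will be able to earn standardized alcohol exposures by performing a button pressing task". Section 3.2 names the two self-administration outcomes for Aim 2: "less cumulative work for alcohol on the progressive ratio task, and reduced overall alcohol exposure as reflected by the breath alcohol concentration (BrAC) curve". Section 12 repeats the prediction without any condition on how strongly the alcohol is felt: "Participants will demonstrate reduced cumulative work for alcohol rewards and less overall alcohol exposure under OT compared to PL".

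Aim 1 predicts reduced tolerance. In Section 12 it takes the form that "participants exhibit greater effects of alcohol when tested with OT compared to PL and each with respect to its own baseline assessment". Section 1.0 explains what tolerance means for intake: "achieving intoxication requires ingestion of steadily increasing amounts of alcohol, a process referred to as tolerance formation".

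Section 2.0 links the two ideas ("The project will examine whether OT reverses tolerance and associated alcohol seeking in humans") but lets each stand alone: "Evidence supporting either outcome would indicate that OT has a potentially novel therapeutic effect". Under Hypothesis 2 in Section 12, a change in any one listed measure is enough. One listed measure is the same sentence that appears under Hypothesis 1: weaker subjective effects and higher craving under placebo (PL).

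In the self-administration arm, Section 7.0 schedules subjective ratings before the first dose, just before alcohol becomes available, "and at 20 min intervals throughout the session, timed with alcohol reward increments when possible". The only analysis described is OT–PL paired t-tests, allowing for baseline as appropriate.

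**The concern.** On the protocol's own definition, lower tolerance means that less alcohol is needed for the same intoxication. If OT does what Aim 1 predicts, a participant aiming for a familiar level of intoxication could get there with fewer rewards. Work and BrAC would fall although the wish to be intoxicated had not changed, and Section 12 would record this as reduced motivation.

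The design safeguards do not cover it. The adaptive task described with Figure 5 holds the success rate constant despite intoxication, so it deals with impaired performance and not with a reduced need for alcohol. The water option supplies an alternative reward but does not tell satiety from loss of interest. Each participant does either the clamp or self-administration (Section 5.0), so clamp results cannot show within a person whether sensitivity explains lower intake.

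At stake is what the follow-on study is told. Section 12 gives the primary goal as producing data to support a larger study of tolerance and/or motivation. A sensitivity effect labelled as a motivation effect would point that study at the wrong mechanism.

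**Working it through.** The plan gives no figure to reproduce for this point. The check asks whether both Aim 2 self-administration outcomes can move as predicted with motivation held fixed, and whether they must.

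**Inputs from Section 7.0.** Each alcohol reward raises BrAC by 10 mg/dL over 2.5 min; BrAC then falls by 0.8 mg/dL/min; the session lasts 150 min; the safety limit is 180 mg/dL.

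**Assumptions not in the documents.** Felt effect = s × BrAC, with s = 1 under PL and s > 1 under OT. Time spent working is ignored. The reward schedule is not given, so the cost of the k-th reward is taken either as k (total n(n+1)/2) or as rising 10% per reward (total (1.1ⁿ − 1)/0.1).

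**Model A: titration to a fixed effect.** A reward is taken whenever BrAC + 10 ≤ T under PL, or ≤ T/s under OT. Motivation is the same in both sessions. For s = 1.2:

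| T (mg/dL) | Rewards PL → OT | Mean BrAC ratio | Work ratio (linear / 10%) | Mean rating ratio |
|---|---|---|---|---|
| 60 | 15 → 14 | 0.83 | 0.88 / 0.88 | 0.99 |
| 80 | 16 → 15 | 0.83 | 0.88 / 0.88 | 1.00 |
| 100 | 18 → 17 | 0.83 | 0.89 / 0.89 | 1.00 |
| 120 | 20 → 18 | 0.84 | 0.81 / 0.80 | 1.01 |
| 150 | 22 → 20 | 0.85 | 0.83 / 0.80 | 1.02 |

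Example of linear work at T = 120: 18 × 19/2 = 171 against 20 × 21/2 = 210, and 171/210 = 0.81.

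Across the same targets:
- s = 1.1: mean BrAC falls 8–10%, rewards fall by 0–1, and work falls 0–12.5%.
- s = 1.3: mean BrAC falls 22–25%, rewards fall by 1–3, and work falls 12–29%.

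The rating ratio near 1 is built into this model, because the rating is s × BrAC and BrAC is held near T/s. It shows what pure titration would look like and is not a finding.

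**Model B: work cost sets the stopping point.** Suppose the participant stops after 14 rewards whatever the felt effect, taking them without pause.
- 14 rewards: 35 min up to 140 mg/dL, then 115 min down by 92 to 48. Mean BrAC = (35 × 140/2 + 115 × (140 + 48)/2)/150 = 13,260/150 = 88.4.
- 13 rewards: (32.5 × 130/2 + 117.5 × (130 + 36)/2)/150 = 11,865/150 = 79.1.
- 12 rewards: (30 × 120/2 + 120 × (120 + 24)/2)/150 = 10,440/150 = 69.6.

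Three cases follow:
- Sensitivity up 20%, limit still 14: work ratio 1.00 and BrAC ratio 1.00. Tolerance alone does nothing to either outcome.
- Motivation truly falls from 14 to 12 and sensitivity rises 30%: BrAC ratio 69.6/88.4 = 0.79; rating ratio 1.3 × 0.787 = 1.02.
- Motivation truly falls from 14 to 13 and sensitivity rises 20%: BrAC ratio 79.1/88.4 = 0.895; rating ratio 1.2 × 0.895 = 1.07.

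**Reading A and B together.** Lower work and BrAC with unchanged ratings is what greater sensitivity alone gives in Model A, and what a real fall in motivation plus greater sensitivity gives in Model B. If motivation alone fell, with sensitivity unchanged, the rating would fall in proportion to BrAC. Ratings beside BrAC are therefore informative, but they do not classify mixed cases.

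**The case against.** The strongest reply is that nothing in the documents says participants titrate to a fixed effect. The Figure 4 legend says behaviour is limited by the safety limit and by the rising work demand, and a progressive ratio is built so that cost sets the stopping point. Section 1.0 also describes later-stage drinking as compulsive rather than pleasure-seeking. This stands. A reader might infer that reduced tolerance *would* by itself cut intake; the documents support only *could*. Model B gives no effect, and a stronger effect per reward might raise work and hide a true fall in motivation.

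A reader might also infer that one Aim 1 result is counted twice. The documents do not support that for the self-administration outcome: the two arms are different people, no rule adds the aims together, and Section 2.0 openly ties alcohol seeking to tolerance. What remains is a label: an intake outcome is called a direct measure of motivation. The literal overlap is narrower, namely the subjective-effects sentence that Section 12 lists under both hypotheses.

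Nor is it right that the trial has no cleaner evidence on motivation. The purchase task and craving are assessed in the clamp arm after OT or PL but before alcohol, and again at a matched 60 mg/dL, where self-titration cannot operate. They do not repair the reading of work and exposure.

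Finally, this is an exploratory pilot with a minimum of 5 per arm, so elaborate modelling would be out of proportion. That argues for descriptive reporting and careful wording, not for leaving the claim as it is.

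**Conclusion.** The concern holds in limited form. Lower work or exposure under OT shows reduced alcohol seeking or intake. It does not by itself show reduced motivation, because the effect that Aim 1 predicts could produce it. Under titration to a fixed effect, a 20% gain in sensitivity is enough to lower mean BrAC by 15–17% and work by about 11–20%; under a work limit the effect is nil. Which model applies is unknown, and the size depends on an assumed target, an assumed linear effect and an assumed reward schedule.

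Separately, Section 12 lets stronger subjective effects under OT suffice for Hypothesis 2. That is the Aim 1 prediction and says nothing specific about motivation; Section 3.2 lists craving for Aim 2, not subjective effects.

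It may be tempting to require that ratings fall before Aim 2 counts as supported. That goes too far. Such a rule would reject both true falls in motivation shown under Model B (rating ratios 1.02 and 1.07), would contradict the present Hypothesis 2 sentence, and would rest on small rating differences in about 5 people.

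**What to change.** 1. **Section 12, Aim 2 self-administration.** For each session, report the mean change in subjective-effect rating from the assessment just before alcohol, averaged over the 20-min assessments, and the mean BrAC at the same times. Give the OT–PL paired differences with intervals, beside cumulative work and exposure, as description. State in advance whether BrAC is the measured or the system-estimated value, since Section 7.0 provides only occasional breath samples.
2. **Section 2.2.** Delete the word *directly*.
3. **Section 3.2.** State that lower work or exposure shows reduced alcohol seeking or intake. Add that when ratings are not lower despite a lower BrAC, greater sensitivity, reduced motivation or both may explain it, so the result is not attributed to motivation alone.
4. **Section 12, Hypothesis 2.** Remove the prediction of stronger subjective effects under OT and keep craving. Match the mention of subjective perception in Section 2.2.
5. Do not add a rule that Aim 2 is supported only if ratings fall.

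The cost is wording and a short table from data already collected, with no new visits or procedures. The price is a narrower Aim 2 claim, and with about 5 participants per arm the separation stays descriptive.
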